2.4. Endpoints

The study endpoints are provided in [Table 4](#).

Table 4 Study Objectives and Corresponding Endpoints

Primary Objective:	Endpoint/Variable:
Part A: Determine the RP2D and schedule of BDTX-189 administered PO in patients with advanced solid malignancies	Incidence and severity of TEAEs, including DLTs, graded according to NCI CTCAE, Version 5.0
Part B: Assess the antitumor activity of BDTX-189 as a single agent in patients with allosteric [REDACTED] mutations, including [REDACTED] mutations	Objective response defined as either a CR or PR, as determined by BICR and per RECIST version 1.1 based on CT or MRI scans
Secondary Objectives:	Endpoint/Variable:
Part A and B: Assess the safety and tolerability of BDTX-189 as a single oral agent	Incidence of TEAEs; changes in clinical laboratory parameters, vital signs, ECG parameters, cardiac function, and physical examination results
Part A and B: Investigate the PK of BDTX-189 using PopPK methods and explore correlations between PK, response, and/or safety findings	PopPK parameters: Cl/F, Vd/F, and Ka for BDTX-189. Cl/F will be used to generate estimates of BDTX-189 AUC. Possible PK/safety and PK/efficacy correlations, and covariate analysis of intrinsic/extrinsic factors
Part A: Establish the PK of BDTX-189 and circulating metabolite profile after a single dose and at steady-state	PK parameter estimates of BDTX-189 generated from plasma concentration-time data (e.g., C_{max} , T_{max} , AUC, and $t_{1/2}$)
Part A: Evaluate the preliminary efficacy and antitumor activity of BDTX-189 as a single oral agent	Investigator-assessed objective response, DOR, DCR, PFS as determined by RECIST v1.1, and OS (for Safety Expansion portion).
Part A: Assess the effect of food on the PK of BDTX-189	PK parameter estimates of BDTX-189 generated from plasma concentration-time data (e.g., C_{max} , T_{max} , AUC, $t_{1/2}$, Cl/F, and Vd/F). Fed/fasted geometric least squares mean ratio and 90% CI for BDTX-189 C_{max} and AUC
Part B: Assess additional measures of efficacy and antitumor activity of BDTX-189 as a single agent	Objective response (Investigator assessed), DOR (Investigator and BICR assessed), DCR (Investigator and BICR assessed), PFS (Investigator and BICR assessed) per RECIST v1.1, and OS
Part B assess patient outcome by evaluation of PROs	Change from baseline in the FACT-G subscales, NCCN-FACT FBSI-16 subscales, NCCN-FACT FLSI-17 subscales, EQ-5D-5L, PROMIS physical function score, and NCI-CTCAE scores

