Patients will be evaluated for response to treatment after 2 cycles of treatment. Response will be assessed at 6-week intervals (± 3 days) during the first 24 weeks (8 cycles) of study treatment. Thereafter, patients will be evaluated for response to treatment every 12 weeks (± 7 days), at the EOT visit (if not performed within the previous 4 weeks), and at the discretion of the Investigator. Patients with PD or unacceptable toxicity should be discontinued from the study; patients with SD or response to therapy will continue treatment. However, patients who are receiving clinical benefit in the opinion of the treating Investigator may be allowed to stay on study beyond initial radiological progression after consultation with the Medical Monitor if it is felt that it is in the patient's best interest. The assessments to be performed at this time are specified in [Appendix B](#). All target and non-target lesions documented at screening must be assessed. Please refer to Section [7](#) for further instructions on evaluating response (e.g., PD, SD).

The following assessments will be performed if abnormal at baseline or if clinically indicated:

- CT scan or MRI of chest, abdomen, and pelvis plus any other sites of known disease.
- CT scan head/MRI brain if history of CNS metastasis.

Investigators must ensure that images of all chest and abdomen CT/MRI scans for patients enrolled in Part B are available for transmission to the Sponsor for a future central reading by a BICR committee depending on preliminary efficacy results from Part A (see separate imaging charter).

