9.2. Estimands

The primary estimand for Part A is the rate at which DLTs occur after treatment with BDTX-189 when administered either QD or BID. It is further described by the following attributes:

- Population: Patients with advanced solid malignancies as reflected by the inclusion/exclusion criteria outlined in Sections 3.1 and 3.2.
- Variable: DLTs, as defined in Section 4.3.2, occurring during the first 21 days of treatment (i.e., Cycle 1).
- Population-level summary: DLT rate, which is defined as the proportion of patients who experience a DLT during Cycle 1. Separate summaries will be estimated for each evaluated dose level of BDTX-189.
- Intercurrent events: Estimation will be based on the hypothetical situation that all patients either receive at least 75% of their planned doses of BDTX-189 during their first 21 days of treatment or experience a DLT during their first 21 days of treatment (i.e. are considered DLT-evaluable). Patients who are DLT-evaluable will be included in the calculation of the DLT rate. Additional patients will be enrolled, if necessary, to ensure an adequate number of DLT-evaluable patients.

The primary estimand for Part B is the effect of BDTX-189, when administered at the RP2D, on objective response rate as assessed by BICR and per RECIST v1.1. It is described by the following attributes:

- Population: Patients with solid tumors containing mutations falling into one of the MTC-A through MTC-G groupings as reflected by the inclusion/exclusion criteria outlined in Sections 3.1 and 3.2.
- Variable: Objective responses defined as CR or PR as assessed by BICR and per RECIST v1.1, which occur from the date of first dose of study treatment until the date of the first documentation of PD, death or start of new anti-cancer therapy. Objective responses must be confirmed by repeat assessments performed at least 4 weeks later.

- Population-level summary: Objective response rate, defined as the proportion of patients in the analysis population with an objective response. Separate summaries will be estimated for various combinations of MTC groupings and tumor types.
- Intercurrent events: Estimation will be based on a “while on treatment” strategy. Patients who do not have a post-baseline tumor assessment or patients who receive subsequent anti-cancer therapies, have PD, die, or otherwise stop tumor assessments prior to experiencing a CR or PR will be considered non-responders.

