9.5.3. Efficacy Analysis

The Investigator-assessed objective response is a secondary endpoint for Part A. BICR-assessed objective response is a primary endpoint for Part B. Secondary objectives of Part B include evaluating the Investigator-assessed objective response, and evaluating both the Investigator and BICR-assessed duration of response (DOR), disease control rate (DCR), and PFS as evidence of the antitumor activity of BDTX-189. Evidence of antitumor activity for ORR, DOR, DCR, and PFS will be determined by RECIST v1.1. OS is also a secondary endpoint for Part B.

- Objective Response Rate (ORR), defined as the proportion of patients with a best overall response of CR or PR recorded from baseline until PD, start of subsequent anti-cancer therapy, or death due to any cause according to the RECIST Version 1.1 criteria (see [Appendix B](#)). The Part B primary endpoint will be based on the confirmed ORR (i.e., 2 CRs or PRs at least 4 weeks apart). Unconfirmed best overall response and response rates will also be summarized.
- Duration of Response (DOR), defined as the time between first documentation of a response (CR or PR) and first evidence of PD according to RECIST v1.1 or death due to any cause. In case a patient does not have progression or death, DOR is censored at the date of last adequate tumor assessment (defined as an assessment of CR, PR, or SD). Duration of response analysis will include only the responders.
- Disease Control Rate (DCR) is defined as the proportion of patients with a best overall response of CR, PR, or SD.
- Progression-Free Survival (PFS), defined as the time from the first day of study drug administration to PD as defined by the RECIST Version 1.1 criteria, or death. Patients who are alive and free from PD will be censored at the date of last adequate tumor assessment.
- Overall Survival (OS), defined as the time from the first day of study drug administration to death. Patients who are alive will be censored at the last date the patient was known to be alive.

For ORR and DCR, patients without an adequate post-baseline tumor assessment will be classified as NE and considered non-responders. ORR estimates and the associated 95% CIs (based on exact binomial distributions) in each cohort/subgroup will be calculated.

For PFS and OS, Kaplan-Meier curves will be generated, and the median time-to-event and the associated 2-sided 95% CIs will be provided.

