10.3.3. Blinded Independent Central Review Committee

A blinded independent central review (BICR) committee will review all available tumor assessment scans for patients enrolled to Part B of this study. Each image will be independently reviewed. The process for review and adjudication of the images will be provided in the imaging review charter (IRC).

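### Section 5.3.3 ties the Part B central reading to Part A results and names only chest and abdomen images for it, against an unconditional BICR primary endpoint and a BICR that reads all available scans

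*Combined protocol and SAP*

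**What the plan says.** Section 5.3.3 (Response Assessments) contains the site instruction at issue. On which images: "Investigators must ensure that images of all chest and abdomen CT/MRI scans for patients enrolled in Part B are available for transmission". On their purpose: "available for transmission to the Sponsor for a future central reading by a BICR committee depending on preliminary efficacy results from Part A". The sentence ends with a pointer to a separate imaging charter. The same section requires every target and non-target lesion recorded at screening to be assessed. It introduces the chest, abdomen and pelvis scans with a condition: "The following assessments will be performed if abnormal at baseline or if clinically indicated".

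Other current text treats the central reading as fixed:

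- Table 4, Part B primary endpoint: "Objective response defined as either a CR or PR, as determined by BICR and per RECIST version 1.1 based on CT or MRI scans".
- Table 4, Part B secondary endpoints: "DOR (Investigator and BICR assessed), DCR (Investigator and BICR assessed), PFS (Investigator and BICR assessed) per RECIST v1.1".
- Section 9.2: "The primary estimand for Part B is the effect of BDTX-189, when administered at the RP2D, on objective response rate as assessed by BICR".
- Section 9.5.3: "BICR-assessed objective response is a primary endpoint for Part B".
- Section 10.3.3, on the committee: it "will review all available tumor assessment scans for patients enrolled to Part B of this study".

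Table 3 footnote s schedules Part B imaging of the chest, abdomen and pelvis and of any other site with known disease at baseline. It attaches no condition. Table 1 footnote w and Table 2 footnote t schedule the same regions in Part A.

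**The concern.** A primary endpoint cannot be both fixed in advance and dependent on results from another part of the study. Section 5.3.3 gives no trigger, threshold or decision-maker for the dependence, and nothing elsewhere in the documents supplies one. If the reading did not take place, the Part B primary endpoint as defined would have no data. The rejection rules could then be applied only to Investigator-assessed response, which is a secondary endpoint.

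The image list raises a separate problem. A central reader who receives only the chest and abdomen sees less disease than the site does. Response and progression under RECIST depend on all target and non-target lesions and on new lesions anywhere, so some central calls could rest on incomplete disease. Cohort 4 includes cervical cancer, and Cohort 5 takes any solid tumor type.

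**Working it through.** No figure in the plan is disputed, so the check is mainly a comparison of texts. The error rates are reproduced first to show that they are not in question.

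**Error rates.** Inputs are the stage sizes and boundaries in Section 9.3.2. Let f_k(x) be the probability of x cumulative responses at stage k without having stopped earlier, m_k the patients added at stage k, and r_k the futility boundary. Then f_k(x) = Σ over y > r_(k−1) of f_(k−1)(y) · C(m_k, x−y) · p^(x−y) · (1−p)^(m_k−x+y). The probability of rejecting the null is the sum of the last f over x above the final boundary. Two stage 1 values serve as a check: 0.825^15 = 0.0558 (Table 12) and 0.95^10 = 0.5987 (Tables 13 and 14).

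| Group | Stop if responses ≤ | Reject at null ORR | Reject at target ORR |
|---|---|---|---|
| Cohorts 1, 2 | 0/15, 6/31, 20/85 | 0.0459 at 17.5% | 0.8008 at 30% |
| Cohort 3, 4 subgroups | 0/10, 3/29 | 0.0468 at 5% | 0.8011 at 20% |
| Cohort 5 | 3/30, 13/89 | 0.0478 at 10% | 0.8018 at 20% |

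All agree with Tables 12 to 15 to four decimals. They describe a response count once it exists. They say nothing about who reads the scans or which images are read.

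**Reach of the condition.**

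- Planned Part B patients: 85 + 85 + 5×29 + 3×29 + 89 = 85 + 85 + 145 + 87 + 89 = 491, as stated.
- Separate tests: 1 + 1 + 5 + 3 + 1 = 11.
- Final rules, all counts of primary-endpoint responses: at least 21/85, 4/29 and 14/89.

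The 491 is a maximum. Cohorts and subgroups can stop for futility, and the sponsor may cap enrollment.

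**Condition on the reading.** Section 5.3.3 makes it depend on Part A efficacy. Table 4 and Sections 9.2, 9.5.3 and 10.3.3 attach no condition. The clause cannot easily be read as a gate on opening Part B, because the sentence concerns patients already enrolled in Part B.

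**Image scope.** Three descriptions of the images differ:

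1. Imaged (Table 3 footnote s): chest, abdomen, pelvis, other known sites.
2. Reviewed by the BICR (Section 10.3.3): all available scans.
3. To be made available by sites (Section 5.3.3): chest and abdomen.

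Item 2 does not repair item 3, because Section 5.3.3 is the text that tells sites what to make available.

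**Consequence for the endpoint.** Under Appendix B a new lesion is PD whatever the target lesions show. Section 9.2 counts responses only until PD. A new pelvic lesion that the BICR never sees could therefore leave a response standing that should not. Conversely, the Appendix B table gives an overall response of NE when target lesions are not all evaluated and nothing shows PD, and Section 9.5.3 counts a patient with no adequate post-baseline assessment as a non-responder. The direction of any error is therefore not fixed. Its size cannot be computed, because the documents do not give the share of patients with disease outside the chest and abdomen.

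**The case against.** The strongest reply is that the governing text is clear and one subordinate clause should not be read against it. The endpoint table, the estimand, the efficacy section and the section that sets up the committee all agree. The amendment summary gives the determination of ORR and PFS as the reason for adding Section 10.3.3. The duty on sites is also unconditional: they must have the named images available whatever Part A shows, and only the later reading carries the clause. On a milder view the clause governs only when the reading or transfer happens. On image scope, the sentence does not say that other regions are excluded, and it refers to an imaging charter that may list them.

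Much of this stands. It makes unreconciled wording more likely than a plan to do without the central reading. It does not remove the conflict. The milder view still leaves a timing rule with no stated trigger, and it does not explain why the pelvis and other sites are missing. A charter can direct what is collected, but it does not make the protocol consistent for a site working from Section 5.3.3.

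A reader might go further in several ways that the documents do not support:

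- *That images will be lost.* Section 12.3 requires source documents to be kept. The issue is what reaches the BICR, not what the site retains.
- *That calling the reading future is itself an error.* Section 4.1 shows that Part B had yet to open when this version was written.
- *That Cohort 5 plus the cervical subgroup measures the patients affected.* Many Cohort 5 patients need have no pelvic disease, and patients in other cohorts may have some.
- *That Part B scans will be skipped because of the baseline-abnormality condition.* All Part B patients have measurable disease (inclusion criterion 17), and Sections 4.4 and 5.1 point to the Schedule of Assessments.
- *That the baseline minimum in Table 3 footnote t is wrong because it omits the pelvis.* It is a minimum that adds other sites of known disease, and Tables 1 and 2 carry the same wording.

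**Conclusion.** The inconsistency is real and should be corrected. Section 5.3.3 conflicts with Table 4 and Sections 9.2, 9.5.3 and 10.3.3 on whether the Part B central reading is conditional. It conflicts with Section 10.3.3 and Table 3 footnote s on which images the reading covers. Confidence is high on the first conflict. It is lower on the practical effect of the second, because the charter could not be checked.

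The condition bears on the primary endpoint of all 11 tests. The documents do not support concluding that the primary endpoint will go unread or that ORR will be biased by any stated amount. Both consequences assume that Section 5.3.3 is followed literally over the governing sections, and the second also assumes that the charter does not widen the image set. Design, sample size and error rates are unaffected. The condition on the chest, abdomen and pelvis scans is a minor wording conflict with Tables 1 to 3.

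**What to change.** In Section 5.3.3:

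1. Delete the clause that makes the central reading depend on preliminary Part A efficacy.
2. Replace the chest and abdomen image list with a requirement that all tumor-assessment images of Part B patients, for every region imaged, be made available to the BICR, in line with Section 10.3.3.
3. Check that the imaging charter agrees on both points.
4. As a tidy-up, replace the condition on the chest, abdomen and pelvis scans with a reference to the Schedule of Assessments (Tables 1 to 3). The separate condition on head CT or brain MRI can stay.

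The cost is a text edit in one section and a check of the charter. Sites may have more images to transmit. No scans are added, because Tables 1 to 3 already schedule them. Correcting the text before Part B enrolls is easier than recovering missing images later from about 80 centers.

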5.3.4. Patient Reported Outcomes (Part B only)

Patient reported outcomes (PROs) will be collected at C1D1, C1D8 and on Day 1 of every Cycle C2-C9. After C9D1 continue to collect electronic patient reported outcomes (ePROs) every 3 months (\pm 14 days), at the EOT visit, and 30-Day Safety Follow-up visit. Continue to collect ePROs even if the patient has discontinued taking the study drug until subsequent anti-tumor therapy is initiated. PROs should be provided to the patient as soon as they arrive at the site for their visit, before any other assessments are performed.

Table 9 ePRO Assessments (Part B only)

Assessments	NSCLC	Breast Cancer	Other Cancers
NCCN FACT FBSI-16 (16 questions)		X	
NCCN-FACT FLSI-17 (17 questions)	X		
FACT-G (27 questions)^a	X	X	X
EQ-5D-5L (5 questions)	X	X	X
Physical Function PROMIS Short Form 8c (8 questions)	X	X	X
NCI-CTCAE (14 questions)	X	X	X

Abbreviations: CTCAE = common terminology criteria for adverse events; ePRO = electronic patient reported outcome; EQ-5D-5L = EuroQol Group's 5-domain 5-level questionnaire; FACT = functional assessment of cancer therapy; FACT-G = functional assessment of cancer therapy-general; FBSI = functional Assessment of Cancer Therapy Breast Symptom Index; FLSI = Functional Assessment of Cancer Therapy Lung Cancer Symptom Index; NCI = national cancer institute; NCCN = national comprehensive cancer network; PROMIS = Patient Reported Outcomes Measurement Information System.

a For Cohorts 1-3: Patients will answer only 13 of the 27 questions in the FACT-G questionnaire.

5.4. Follow-up Periods and Study Completion

5.4.1. End-of-Treatment Visit

The EOT visit will be performed as soon as possible (preferably within 3 days but no later than 14 days) after permanent discontinuation of the study treatment or when the Investigator decided with the patient to permanently discontinue the study treatment or when the Investigator became aware that the study treatment had been discontinued. The assessments of the EOT visit will then be performed instead of at the next planned visit. If the patient finishes treatment without having PD, tumor assessment/imaging must be performed at the time of treatment discontinuation unless it has been done within the past 4 weeks.

5.4.2. 30-day Safety Follow-up Visit

All patients will be followed during the off-treatment period until all treatment-related toxicity has resolved, or for at least 30 days (\pm 3 days) post-study drug discontinuation, or until the start

of another anti-cancer treatment, in which case this visit should occur before the start of subsequent therapy. Any concomitant medications received up to 30 days after the last dose of study medication should be recorded. For Part B and the Safety Expansion portion of Part A subsequent anticancer therapy will continue to be collected as outlined in Table 2 and Table 3.

Thirty-day Safety Follow-up visit assessments do not need to be repeated if a new anti-cancer therapy was initiated within 7 days of the EOT visit, unless further study drug was administered or there was a new abnormal test result when last assessed (including an abnormal test result which had worsened from previous). If the EOT visit is more than 30 days after the last dose of study treatment, the 30-Day Safety Follow-up visit is not required.

5.4.3. Extended Follow-up Period (Safety Expansion and Part B)

For patients participating in Safety Expansion portion of Part A and all patients in Part B, additional follow-up for OS, PFS, and the first subsequent anti-cancer therapy after the 30-Day Safety Follow-up visit will be performed every 3 months (± 14 days) until 2 years after the first study drug dose if the patient has stopped treatment prior to PD based on RECIST Version 1.1 as assessed by the Investigator (see [Appendix B](#)) or another withdrawal criterion is met:

- Start of a new anti-cancer therapy.
- Lost to follow-up.
- Death.
- End of the whole study.

Follow-up information for OS may be obtained by phone.

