^u Archival tissue sample is required for patients in the Safety Expansion who have allosteric *ErbB* mutations and archival tissue available; tissue block is preferred. In the event that a tissue block is unavailable, 12-20 formalin-fixed paraffin-embedded unstained slides may be submitted. If there is not enough archival tumor tissue, a new tumor tissue biopsy sample must be obtained during screening, prior to starting study treatment. (See Section [5.7.1](#))

^v May be performed any time within 28 days prior to C1D1 and includes assessments completed at the clinical site as part of standard of care, and prior to the signing of the informed consent, if the assessments were performed in compliance with the protocol requirements. Baseline assessment must include CT or MRI imaging of the chest and abdomen, through the level of the adrenals, and brain, if clinically indicated, as well as other sites of known disease.

^w A smaller and reformulated 200 mg tablet may be introduced and supplied to some patients during the Safety Expansion of Part A; these tablets will be available to all patients enrolling onto Part B. Patients in Part A who initiated treatment with the larger-200 mg tablet may be switched to the smaller and reformulated 200 mg tablet at the beginning of their subsequent cycles. Detailed PK sampling will be collected on Day 15 (i.e., after 14 days of daily treatment with the smaller 200 mg tablet) of that subsequent cycle according to [Table 8](#).

^x From the 30-Day Safety Follow-up visit, follow-up for OS, PFS, and first subsequent anti-cancer therapy, if available, will be obtained every 3 months (\pm 14 days) until 2 years after the patient's first dose of study drug, death, loss to follow-up, withdrawal of consent, or end of the whole trial. Follow-up information about overall survival may be obtained by phone.

Table 3 BDTX-189-01 Schedule of Assessments Part B

Flow Chart (Part B) Study period	Screening	Part B BDTX-189 Treatment Period									
Study Procedures ^a		Cycle 1			Cycle 2 (±2 days)		Cycle 3, 4, 5 and every other cycle thereafter (±2 days)	End of Treatment ^c	30-Day Safety Follow-up Visit ^d	Unscheduled Visits ^e	PFS/OS ^u
Study Day	≤28 days prior to C1D1	1 ^b	8	15	1	8	15	1	Within 3 days of decision to discontinue study drug	30 days after last dose (±3)	
Informed consent	X ^f										
Inclusion / exclusion criteria	X										
Medical and disease history	X										
Demographics	X										

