- ^s Tumor assessment (CT or MRI of chest, abdomen, and pelvis, plus other sites of known disease at baseline) will be performed every 6 weeks for the first 8 cycles, and then every 12 weeks thereafter. Imaging should be completed within a window of -3 days prior to D1 of odd cycles and should be reviewed before study drug administration on D1 for dosing determination. Patients who discontinue treatment for reasons other than PD will undergo tumor assessment in accordance with the original schedule relative to C1D1. Tumor assessment/imaging must be performed at the time of treatment discontinuation, unless it has been done within the past 4 weeks. If disease progression according to RECIST (version 1.1) is documented at any time, no further tumor/response assessment will be required.
- ^t May be performed any time within 28 days prior to C1D1 and includes assessments completed at the clinical site as part of standard of care, and prior to the signing of the informed consent, if the assessments were performed in compliance with the protocol requirements. Baseline assessment must include CT or MRI imaging of the chest and abdomen, through the level of the adrenals, and brain, if clinically indicated, as well as other sites of known disease.
- ^u From the 30-Day Safety Follow-up visit, follow-up for OS, PFS, and first subsequent anti-cancer therapy, if available, will be obtained every 3 months (\pm 14 days) until 2 years after the first dose of study drug, death, loss to follow-up, withdrawal of consent, or end of the whole trial. Follow-up information about overall survival may be obtained by phone.
- ^v Archival tissue sample is mandatory for patients in Part B who have archival tissue available; a tissue block is preferred. In the event that a tissue block is unavailable, 12-20 formalin-fixed paraffin-embedded unstained slides may be submitted. If there is not enough archival tumor tissue, a new tumor tissue biopsy sample must be obtained during screening, prior to starting study treatment. (See Section [5.7.1](#)).

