4.5. Concomitant Medications

Patients will be asked about prior medications during screening and instructed not to take any additional medications during the course of the study without prior consultation with the study team. At each visit, the patient will be asked about any new medications he or she is taking or has taken from 14 days prior to receiving their first dose of study drug until the 30-Day Safety Follow-up visit. Additionally, for the Safety Expansion portion of Part A and Part B, first subsequent anticancer therapy, will be collected as part of PFS/overall survival (OS), from the 30-day Safety Follow-up visit, and will be obtained every 3 months (± 14 days) until 2 years after the first study drug dose, death, loss to follow-up, withdrawal of consent, or end of the whole trial.

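### Section 5.4.3 stops survival follow-up at progression or new therapy, while Tables 2 and 3 do not; followed as written, it loses post-progression deaths

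*Combined protocol and SAP*

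**What the plan says.** Section 5.4.3 covers the Safety Expansion and "all patients in Part B, additional follow-up for OS, PFS, and the first subsequent anti-cancer therapy", all in one sentence. It sets 3-monthly contact "until 2 years after the first study drug dose if the patient has stopped treatment prior to PD based on RECIST Version 1.1" "or another withdrawal criterion is met" (the words between name the Investigator as assessor). The list that follows begins with "Start of a new anti-cancer therapy". OS has no rule of its own, beyond a line allowing the information to be collected by phone.

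The schedules of assessments say something else. Table 2 footnote x (Safety Expansion) follows the same three items until 2 years after the "first dose of study drug, death, loss to follow-up, withdrawal of consent, or end of the whole trial". Table 3 footnote u (Part B) runs "until 2 years after the first dose of study drug, death, loss to follow-up, withdrawal of consent, or end of the whole trial". Section 4.5, on collection of first subsequent therapy, runs "until 2 years after the first study drug dose, death, loss to follow-up, withdrawal of consent, or end of the whole trial". None of the three mentions progression or a new therapy as a limit.

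OS is a secondary endpoint for Part B and for the Safety Expansion (Table 4). Section 9.5.3 defines it as time from first dose to death, censors living patients when last known alive, and plans Kaplan-Meier curves and medians with 95% CIs.

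**The concern.** Progression (PD) is the planned route off treatment (Section 4.4). A patient who stops because of PD does not meet the 5.4.3 condition, so on a literal reading nobody contacts that patient for survival after the 30-day visit. A patient who stops earlier and starts another therapy is also dropped at that point. Under Section 9.5.3 both are censored alive.

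Censoring at or soon after PD depends on prognosis. If patients die faster after PD than before it, the patients left at risk are the healthier ones, and the Kaplan-Meier curve and its median are too high. Deaths that were not collected may be hard to recover at the end of the study.

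**Working it through.** **1. The texts side by side**

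| Source | Condition on PD | New therapy ends follow-up | Consent withdrawal listed |
|---|---|---|---|
| Section 5.4.3 | Yes | Yes | No |
| Table 2 footnote x | No | No | Yes |
| Table 3 footnote u | No | No | Yes |
| Section 4.5 (subsequent therapy only) | No | No | Yes |

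The direct conflict on OS is between 5.4.3 and the two tables; Section 4.5 is supporting. Section 5.4.3 also conflicts with itself: it opens with all Part B patients and then excludes those who stopped at PD, and it collects first subsequent therapy yet ends when that therapy starts. Its sentence parses badly. Whether PD is read as an entry condition or as a stop, OS follow-up of a progressing patient ends no later than PD.

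**2. Is there another route for these deaths?** No. Section 8.1.5 limits reporting from 30 days after the last dose to drug-related SAEs and treatment-related deaths. Section 8.2.5 expects progression deaths to be recorded during survival follow-up, which presupposes that the follow-up takes place.

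**3. Size.** The plan gives no OS assumption, event count or power, so there is no OS figure to reproduce. The following is an illustration with assumed inputs:

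- Median PFS 4.2, 5.5, 8.3 or 14.0 months, exponential. Section 1.1.3 cites these values for other agents.
- Median survival after PD 4, 8 or 12 months, exponential. Assumed.
- Share *f* of PFS events that are deaths: 5% or 20%. Assumed.
- Follow-up to 24 months; under literal 5.4.3, patients with PD are last seen 1 month after PD.

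This gives 4 × 3 × 2 = 24 scenarios. With *a* = ln 2 / (median PFS) and *b* = ln 2 / (median post-PD survival), the death hazard is *f·a* before PD and *b* after it. The ratio *b*/(*f·a*) runs from (4.2/12)/0.20 = 1.8 to (14.0/4)/0.05 = 70.

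Full follow-up: S(t) = e^(−at) + (1−f)·[a/(a−b)]·(e^(−bt) − e^(−at)).

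Literal 5.4.3: no one is censored before month 1, so the curve equals S(1) there. After that, the ratio of post-PD to pre-PD patients still in view is constant, r = (1−f)·a·(e^(a−b) − 1)/(a−b). The observed hazard is h = (f·a + b·r)/(1+r), and the curve is S(1)·e^(−h(t−1)).

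*One scenario in full* (PFS median 5.5, post-PD median 8, f = 20%): a = 0.1260, b = 0.0866, ratio 3.4.
- S(12) = 0.2204 + 0.8 × 3.2 × (0.3536 − 0.2204) = 0.561.
- S(1) = 0.972, r = 0.1028, h = (0.0252 + 0.0866 × 0.1028)/1.1028 = 0.0309.
- Literal curve at 12 months = 0.972 × e^(−11 × 0.0309) = 0.692.

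So 56% is reported as 69%, 13 points too high.

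*All 24 scenarios* (simulation, 200,000 patients each; the closed form gives 6.6 to 31.5 for the first row):

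| Share of patients handled by 5.4.3 | 12-month OS too high by (points) | Median not reached by 24 months |
|---|---|---|
| 0% (tables followed) | 0 | 3 of 24 |
| 100% | 6.7 to 31.4 | 18 of 24 |
| 90% | 5.3 to 24.8 | 14 of 24 |
| 70% | 3.1 to 15.9 | 10 of 24 |
| 50% | 2.0 to 9.8 | 7 of 24 |
| 25% | 0.9 to 4.3 | 5 of 24 |

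The 90% and 70% rows also describe 10% or 30% of patients stopping before PD and so staying in follow-up. Where both medians are reached, the literal one is 4.4 to 13.3 months too long at 100% and 0.4 to 2.7 months at 25%. In a cohort of 85 (the size of Cohorts 1 and 2), 33 to 79 deaths observed by 24 months become 6 to 27 at 100%.

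**4. Controls.** If b = f·a, then h = f·a·(1+r)/(1+r) = b and the bias is zero; simulation agrees within 0.1 point. With a lower hazard after PD (ratio 0.61 to 0.70) the bias is −3.8 to −4.4 points.

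**5. New-therapy stop alone.** Assume 30% to 50% of patients with PD start new therapy 1 to 2 months after PD, with PFS medians of 4.2 to 8.3. The 12-month bias is −3.7 to +2.1 points if treated patients do much better (post-PD median 12 against 3 months), −0.2 to +4.5 if somewhat better (10 against 6), and +0.8 to +9.9 if prognosis is the same. Its sign is not fixed.

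**The case against.** The best defense is that this is a drafting slip, not a chosen rule. Tables 2 and 3 are the operating schedules, and Section 5.1 points to them as the complete schedule. Section 5.4.2 sends subsequent-therapy collection to them, Section 8.2.5 provides forms for progression deaths, and Section 9.5.3 has no censoring at PD. The amendment summary treats 5.4.3 and the two tables as one change. The PD condition makes sense for PFS scans, and 5.4.3 is the outlier. All of that stands as evidence of intent, and the point is best described as an internal inconsistency.

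It does not settle what a site does. No clause gives the tables precedence, and Section 5.3.3 offers support for the narrow reading: "Patients with PD or unacceptable toxicity should be discontinued from the study". That phrase may only mean stopping drug, as Section 3.3 puts it, but it can be read the other way. About 80 centers are planned for Part B.

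The criticism of the numbers is fair in part. No document supports any particular share of patients handled by 5.4.3, the post-PD medians and death shares are assumed, and the 100% row is the extreme case. Section 9.6.1 also triggers a cohort's final analysis once every patient has 6 months of treatment or has stopped, so the 24-month death counts and unreached medians do not describe that analysis. The mechanism behind the 12-month bias is unchanged. OS is descriptive, with no hypothesis attached.

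**Conclusion.** The concern holds. Section 5.4.3 contradicts Table 2 footnote x and Table 3 footnote u on who is followed for survival and when that ends, and a site that follows it as written loses deaths after PD. Where that happens and the death hazard is higher after PD, OS is overstated: in the assumed scenarios by about 7 to 31 points at 12 months if all progressing patients are affected, and by about 1 to 4 points if a quarter of patients are. These sizes rest on assumed survival, not on data for this drug. Sites that use the tables are unaffected. The damage is confined to secondary OS in Part B and the Safety Expansion; ORR, the futility rules and the sample sizes do not change. It should be corrected before Part B follow-up begins.

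**What to change.** Reword 5.4.3 to match Tables 2 and 3 and Section 4.5, with two separate rules:

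- **Survival status and first subsequent therapy:** every treated Safety Expansion and Part B patient, every 3 months, whether or not the patient has progressed or started another therapy, with the same ends as the table footnotes.
- **Tumor assessments for PFS:** keep the PD and new-therapy stops here only.

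Reconcile the 5.3.3 phrase on leaving the study with the Section 3.3 wording on leaving study treatment, so that PD alone does not end survival follow-up. This concerns data collection and leaves the treatment rules as they are.

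A minor, separate point while the text is open: state which scan calendar applies to patients off drug without PD. Table 3 footnote s keeps the original schedule from C1D1, while 5.4.3 and footnote u run 3-monthly from the 30-day visit; Table 2 footnotes t and x need the same check. The intervals differ most before about week 24, when scheduled scans are 6-weekly.

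The cost is a rewritten 5.4.3, one phrase in 5.3.3 and, for the minor point, a sentence in the footnotes. No visits are added: the tables already schedule this contact and survival may be collected by phone.
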